18.2.2. SECONDARY EFFECTIVENESS ENDPOINT

There is one secondary effectiveness endpoint in the study, which is assessing tolerance to astigmatism in IC-8 IOL eyes at 3 months (analysis done on IC-8 IOL eyes with

BCDVA 20/25 or better) by comparing eyes with 1.0 to 1.5 D of preoperative corneal astigmatism (Astigmatism Group 2) to eyes with < 1.0 D of preoperative corneal astigmatism (Astigmatism Group 1):

a. The mean UCDVA from Astigmatism Group 2 is non-inferior to that from Astigmatism Group 1 using a margin of 0.12 logMAR (equivalent to 6 letters on ETDRS chart). The comparison between Astigmatism Group 2 and Astigmatism Group 1 for the mean monocular UCDVA (logMAR) will be performed using a ttest for non-inferiority at $\alpha = 0.05$ (one-sided). The null hypothesis is that the mean acuity in Astigmatism Group 2 is inferior to Astigmatism Group 1 by 0.12 logMAR or more. The alternative hypothesis is that the mean acuity in Astigmatism Group 2 is inferior to Astigmatism Group 1 by less than 0.12 logMAR. Formally put as follows:

$$\begin{split} H_0 &: \mu_T - \mu_C \geq 0.12 \\ H_A &: \mu_T - \mu_C < 0.12 \end{split}$$

Where μ_T is the mean logMAR acuity from Astigmatism Group 2 and μ_C is the mean acuity from Astigmatism Group 1.

The statistical success criterion is when H_0 is rejected by a p-value less than 0.05, demonstrating the mean monocular UCDVA from Astigmatism Group 2 is statistically non-inferior to the mean monocular UCDVA from Astigmatism Group 1 using a margin of 0.12 logMAR.

- b. Scatter plot and regression analysis will be generated to depict the mean uncorrected visual acuities (separately for UCDVA, UCIVA and UCNVA) as a function of preoperative corneal astigmatism.
- c. No claim will be made with regard to comparing IC-8 IOL to the monofocal or monofocal toric IOL.

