9.0 INVESTIGATIONAL PLAN

9.1. OVERVIEW

The study will be conducted in accordance with U.S. Code of Federal Regulations, the Declaration of Helsinki, and all other applicable laws and regulations.

This study will be conducted at approximately 18 to 25 study sites. There will be a total enrollment of 355 test and 120 control subjects to ensure 300 test and 100 control subjects complete one year of postoperative study follow-up. Patients will be consented for three years; the first year will support the PMA with a possibility of two additional years of post-approval follow-up.

Enrollment into one of the two study groups will not be randomized because an IOL with extended range of vision is currently available on the market and patients who desire an extended depth focus should have the opportunity to receive this technology. However, in order to allow for comparison, the two groups should have similar distributions on age, sex, race/ethnicity, pupil size and preoperative corneal astigmatism.

Test group: Subjects will be implanted with the IC-8 IOL in one eye, targeted at 0.75 D of myopia, which is at the near end of the emmetropic limit of the depth of focus, without sacrificing distance visual acuity and an aspheric monofocal or monofocal toric IOL, targeted for emmetropia, defined as plano manifest refractive spherical equivalent (plano MRSE) in the fellow eye.

Control group: Subjects will be bilaterally implanted with an aspheric monofocal or monofocal toric IOL, targeted for emmetropia (plano MRSE), in both eyes.

For both the test group and control groups, the first eye will be implanted with a monofocal or monofocal toric IOL. There will be no restriction on the implantation of the IC-8 IOL to the non-dominant eye only. The investigator may choose the monofocal eye based on the following factors: sighting dominance, patient's occupational and/or recreational needs, history of monovision contact lens wear, habitual spectacle prescription, worst cataract eye, or one eye outside of the IC-8 IOL available powers. The investigator must indicate the primary and secondary factor (if applicable) for choosing the monofocal eye on the source documents and when possible, preoperative and postoperative sighting dominance will be recorded and data will be stratified by eye dominance.

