18.1. ANALYSIS POPULATION

For the primary effectiveness endpoints, the primary analysis population will be an ITT (Intentto-Treat) analysis. The ITT population includes all subjects who are fully enrolled and are binocularly implanted in the study. For the secondary effectiveness endpoint, the primary analysis population will be a mITT (modified Intent-to-Treat) analysis for all eyes implanted with IC-8 IOL and achieving BCDVA 20/25 or better. For eyes that do not have data available at the 3-, 6- or 12-month visits, data will be imputed according to the imputation methods specified in the SAP.

A Per-Protocol (PP) analysis will also be performed on the primary and secondary effectiveness endpoints to support the primary ITT analysis. The PP population will include eyes from binocularly implanted subjects, evaluated within the proper study interval and without major protocol deviations as determined prior to database lock, and evaluated at least two weeks after any SSIs. Major protocol deviations to be excluded from PP analysis are: those related to inclusion, exclusion or qualification criteria, and/or those that have the potential to either positively or negatively affect the primary and secondary study endpoints, including uncorrected or distance-corrected visual acuities, refraction, contrast sensitivity, and are unrelated to the study procedure or the study device; and they will be specified prior to database lock.

PP analyses will only include available data at the time of analysis (i.e., no data imputation). For the primary effectiveness endpoints, the PP population is usually a subset of the ITT population; for the secondary effectiveness endpoint, the PP population is usually a subset of the mITT population.

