18.2. EFFECTIVENESS ANALYSES

All co-primary effectiveness endpoints need to be achieved to claim overall effectiveness success. Therefore no multiplicity adjustment is necessary for primary effectiveness endpoints. The secondary effectiveness endpoint will be tested after the primary effectiveness endpoints have been achieved. The secondary effectiveness endpoint needs to be achieved to support the astigmatism tolerance claim. For the primary effectiveness endpoints, the primary analysis population will be the ITT analysis population. For the secondary effectiveness endpoint, the primary analysis population will be a mITT analysis population. The PP analysis population will also be used on the key effectiveness endpoints to support the primary ITT analyses.

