18.2.3. PROPENSITY SCORE ANALYSIS

As a supplemental analysis for all primary endpoints, propensity score methods will be used to adjust for potential imbalance in measured baseline characteristics between the IC-8 and control patients. All primary analyses described in **section 18.2.1** will be repeated as a stratified analysis, using propensity score quintiles to partition the patients into five strata. Results from these analyses will be reported by stratum and overall. Details are specified in the SAP.

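### The test that decides the astigmatism-tolerance claim compares two non-randomised groups of IC-8 eyes without adjustment, and the planned propensity analysis does not reach it

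*Combined protocol and SAP*

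**What the plan says.** Section 18.2.2 divides the IC-8 eyes by preoperative corneal astigmatism: 1.0 to 1.5 D is Astigmatism Group 2 and under 1.0 D is Group 1. Item a sets the decision rule: "The comparison between Astigmatism Group 2 and Astigmatism Group 1 for the mean monocular UCDVA (logMAR) will be performed using a ttest for non-inferiority". The test is one-sided at 0.05 with a margin of 0.12 logMAR, at 3 months. No covariate or stratum is named. Section 18.1 defines the analysis set as a modified ITT population "for all eyes implanted with IC-8 IOL and achieving BCDVA 20/25 or better".

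The claim depends on this test. Section 18.2 states: "The secondary effectiveness endpoint needs to be achieved to support the astigmatism tolerance claim". Section 18.0 bars additional and supportive comparisons from being used for claims.

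The adjustment described in 18.2.3 is a supplement to the primary endpoints. It addresses imbalance between IC-8 and control patients, and under it the analyses of 18.2.1 "will be repeated as a stratified analysis, using propensity score quintiles to partition the patients into five strata". Two other analyses bear on astigmatism. The regression in 18.2.2b has preoperative astigmatism as its only named predictor and no success rule. The supportive repeat in 18.2.4, item 3c, uses postoperative refractive cylinder with the same test. Neither names a baseline covariate.

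**The concern.** A patient's corneal astigmatism is not allocated, so the design does nothing to make Groups 1 and 2 alike in other respects. If they differ in age, pupil size or anything else related to uncorrected distance acuity, the raw mean difference mixes that with the effect of astigmatism. The mixture is then judged against a fixed margin. A difference that flatters Group 2 makes non-inferiority easier to reach than it should be. A difference the other way can make a tolerant lens fail. Both the reader of the claim and the sponsor are exposed, and no other analysis in the text may carry the claim.

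**Working it through.** **Scope of the planned adjustment.** Section 18.2.3 is limited in two ways: to the endpoints of 18.2.1, and to IC-8 versus control patients. The secondary endpoint is in 18.2.2, and its contrast lies wholly within IC-8 eyes. It falls outside on both counts.

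**The plan's own figures.** Table 3 gives 295 enrolled for 250 completers in Group 1 and 60 for 50 in Group 2. With the 10% attrition and 5% disqualification of section 7.0:
- 250/(0.90 × 0.95) gives 293 and 250/0.85 gives 295.
- 50/(0.90 × 0.95) and 50/0.85 both give 59.

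The targets reproduce to within two patients. No SD, expected difference or power for the secondary endpoint appears in the text, so there is no power figure to reproduce.

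**Inputs.** From the documents: margin 0.12, one-sided alpha 0.05, and 250 versus 50 eyes. These are one-year completer targets; the 3-month set restricted on BCDVA may differ. Assumed: SD 0.10, 0.15 or 0.20 logMAR.

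**Formulas.** The difference is Group 2 minus Group 1, and higher logMAR is worse.
- SE = SD × √(1/250 + 1/50) = SD × 0.1549.
- Largest observed difference that passes = 0.12 − t(0.95; 298 df) × SE.
- Pass probability: noncentral t with 298 df and noncentrality (true difference + bias − 0.12)/SE.

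| Assumed SD | SE | Largest passing difference | True 0.12: bias 0 / −0.02 / −0.04 | True 0.05: bias 0 / +0.02 | True 0: bias 0 / +0.02 / +0.04 |
|---|---|---|---|---|---|
| 0.10 | 0.0155 | 0.094 | 5% / 36% / 82% | 99.8% / 94% | about 100% throughout |
| 0.15 | 0.0232 | 0.082 | 5% / 22% / 53% | 91% / 69% | 100% / 99.6% / 96% |
| 0.20 | 0.0310 | 0.069 | 5% / 16% / 36% | 73% / 49% | 98.7% / 94% / 82% |

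A bias of 0.02 is one ETDRS letter, since the plan equates 0.12 with six.

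**How such a bias could arise.** For a single covariate, bias is roughly its correlation with UCDVA × its standardised imbalance × SD. A correlation of 0.3 and an imbalance of 0.4 SD give 0.012, 0.018 and 0.024 at the three SDs. A correlation of 0.2 and an imbalance of 0.2 SD give only 0.004, 0.006 and 0.008. All of these inputs are illustrative.

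**Precision.** If covariates explain a share R² of the variance, the gain is equivalent to 1/(1 − R²) times as many eyes, ignoring the small cost of imbalance. At SD 0.15 and a true difference of 0.05, power is Φ(0.07/0.0232 − 1.645) = 91.4%. It becomes 93.7% at R² = 0.1 and 95.8% at R² = 0.2. Age alone may explain less. With an assumed slope of 0.002 to 0.005 logMAR per year and an assumed age SD of 6 to 10 years, R² runs from (0.002 × 6/0.15)² = 0.6% to (0.005 × 10/0.15)² = 11%, and power from 91.6% to 93.9%.

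**The case against.** The strongest reply is that the text available for review does not include the SAP. Section 18.0 places full statistical detail there, 18.4 sends stratification and sensitivity analyses there, and 7.0 sends the control of baseline imbalance there. A reader might infer that the plan has no other confounding control, or that age and pupil size go unused. The documents do not establish either. What survives is narrower: a sensitivity analysis in the SAP would not change the success criterion stated in 18.2.2a, which is the raw t-test.

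A reader might also take section 9.1 to require balance here, since it says "the two groups should have similar distributions on age, sex, race/ethnicity, pupil size and preoperative corneal astigmatism". That sentence concerns the test and control arms and says should. Its list includes corneal astigmatism, which cannot be alike in groups defined by it. The protocol does not contradict itself; only the reasoning carries over.

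The design also limits the likely confounders. Macular disease, abnormal pupils and irregular astigmatism are excluded, eyes must reach BCDVA 20/25, the aperture is fixed at 1.36 mm, and UCDVA is tested photopically. This plausibly reduces dependence on age and pupil without removing it: the mask ends at 3.23 mm within a 6 mm optic, and ambient light is about 5 lux. Nothing in the documents shows that age or pupil size differs between the groups, or in which direction. It would therefore be wrong to infer that the test is biased in the lens's favour.

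Finally, the indication covers eyes as they present, so an unadjusted contrast is a defensible estimand. That is fair, and it is a reason to keep reporting the raw test. A claim of tolerance to astigmatism, however, attributes the difference to astigmatism, which the adjusted estimate addresses more directly.

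**Conclusion.** The point holds as a gap that should be closed, not as a demonstrated bias. The claim-bearing test is unadjusted, its groups are not randomised, and 18.2.3 does not reach it. Under the assumed SDs, a one-letter bias favouring Group 2 would turn the 5% error at the margin into about 36% to 16%. The same bias in the other direction would cut the chance of passing at a true difference of 0.05, for example from 91% to 69% at SD 0.15. The size and direction of any real bias are unknown.

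The exposure matters mainly when the true difference is near the margin or partway to it. If the true difference is near zero, an adverse one-letter bias still leaves a pass probability of 94% or more. A reader might infer from the 50 eyes in Group 2 that the test is underpowered. At zero true difference the power is at least 98.7% across the assumed SDs, so sample size is not the weakness. The precision gain from adjustment is modest and depends on an R² that the documents do not give.

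**What to change.** In 18.2.2a, and in the SAP to match, estimate the Group 2 minus Group 1 difference in UCDVA from a linear model with astigmatism group and a short list of baseline covariates fixed before database lock. The list should hold at least age and preoperative photopic pupil size. Declare non-inferiority if the one-sided 95% upper bound is below the unchanged 0.12 logMAR margin. Keep the raw t-test as a sensitivity analysis. If the SAP already holds an adjusted analysis of this contrast, the change is to make it the decision rule.

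The cost is about a sentence in each place and agreement on the covariates. Age and pupil size are already collected before surgery, and no more patients are needed. Pupil size is recorded only to the nearest half millimetre and by differing methods, so adjustment for it will be imperfect. Baseline adjustment will also not fully remove any selection introduced by restricting the analysis to eyes that reach BCDVA 20/25 after surgery.

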18.2.3. PROPENSITY SCORE ANALYSIS

As a supplemental analysis for all primary endpoints, propensity score methods will be used to adjust for potential imbalance in measured baseline characteristics between the IC-8 and control patients. All primary analyses described in **section 18.2.1** will be repeated as a stratified analysis, using propensity score quintiles to partition the patients into five strata. Results from these analyses will be reported by stratum and overall. Details are specified in the SAP.

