7.0 STUDY POPULATION

Potential study subjects will be recruited from patients with bilateral cataracts who plan to undergo crystalline lens removal by phacoemulsification followed by intraocular lens implantation in the capsular bag. Eligibility for the study will be determined at the preoperative visit. If the patient meets all inclusion/exclusion criteria, he or she must give informed consent to be provisionally enrolled in the study as a subject.

To allow for approximately 10% attrition rate over the duration of the one-year study and another 5% disqualification rate for the first implanted eye, a total of 355 test subjects and 120 control subjects will be consented and provisionally enrolled to ensure 300 test and 100 control subjects are available to complete the one-year follow-up to support the PMA.

Each study site (assuming a total of 23 sites) should enroll approximately 15 subjects in the test group and 5 subjects in the control group, but no more than 25% of the total population of the study. The number of subjects intended to be enrolled in the study for each treatment arm (before

the first implanted eye's qualification to complete enrollment) is shown in **Table 3**. Furthermore, based on previous data from the IC-8 IOL European clinical study, the distribution of preexisting corneal astigmatism between 0 and 1.5 D in the intended population consists of roughly 83-85% of patients between 0 to less than 1.0 D and roughly 15-17% of patients between 1.0 to 1.5 D. The anticipated enrollment ratio is thus approximately 5:1 for < 1.0 D of preoperative corneal astigmatism (Astigmatism Group 1) vs. 1.0 to 1.5 D of preoperative corneal astigmatism (Astigmatism Group 1) vs. 1.0 to 1.5 D of preoperative corneal astigmatism group as shown in **Table 3** should reflect the anticipated enrollment by group in the study. The overall enrollment from all sites will be monitored closely to ensure that the enrollment target should be met for each treatment arm and astigmatism group. When each and all targets are met, the sponsor will inform all sites to cease enrollment. More details on controlling the enrollment process for potential imbalance in baseline characteristics is specified in the Statistical Analysis Plan (SAP).

	Astigmatism Group 1** (< 1.0 D of preoperative corneal astigmatism)	Astigmatism Group 2** (1.0 D to 1.5 D of preoperative corneal astigmatism)

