18.0 DATA ANALYSIS METHODS

This section (section 18.0 through 18.4) highlights the key statistical methods and analyses planned for this study. The SAP includes details for all statistical methods, plans, adverse events reporting methods, and sample size calculations for the study.

Some key data and analysis conventions include the following:

For the primary and secondary effectiveness endpoints, the six-month postoperative visit will be the primary analysis time point unless otherwise noted. For the primary safety endpoints, the 12-month study visit will be the primary analysis time point.

Binocular safety and effectiveness analyses will compare the test group and the control group. Monocular safety and effectiveness analyses will compare the IC-8 IOL eyes and the monofocal fellow eyes within the test group. All co-primary effectiveness and safety endpoints have to be met to claim overall effectiveness and safety success. There is one secondary effectiveness endpoint regarding the tolerance to astigmatism in IC-8 IOL eyes, and this endpoint will only be tested when all co-primary effectiveness endpoints have been achieved. Under this plan, type I error rates will be controlled at a significance level of 0.05 per individual hypothesis without adjustment for multiplicity under any family. Other statistical comparisons in the additional analyses and supportive analyses should not be used for the purpose of claims.

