 - a. The mean acuity from the test group is non-inferior to the mean acuity from the control group using a margin of 0.1 logMAR. The comparison between test and control groups for mean binocular UCDVA (logMAR) will be performed using a t-test for non-inferiority at $\alpha = 0.05$ (one-sided). The null hypothesis is that the mean acuity for the test group is inferior to the control group by 0.1 logMAR or more. The alternative hypothesis is that the mean acuity for the test group by less than 0.1 logMAR. Formally put as follows:

$$\begin{split} &H_0{:}\,\mu_T-\mu_C\geq 0.1\\ &H_A{:}\,\mu_T-\mu_C<0.1 \end{split}$$

Where μ_T is the mean logMAR acuity from the IC-8 test group and μ_C is the mean logMAR acuity from the control group.

The statistical success criterion is when H_0 is rejected by a p-value less than 0.05, demonstrating the mean binocular UCDVA from the test group is statistically non-inferior to the mean binocular UCDVA from the control group using a margin of 0.1 logMAR.

- b. At least 50% of test subjects achieve 0.1 or better logMAR [clinical success criteria].
- 4. Monocular distance-corrected intermediate visual acuity (DCIVA) of the IC-8 IOL eyes (at 6 months):
 - a. The mean acuity of the IC-8 IOL eyes is statistically superior to the fellow control eyes in the test group. The comparison between IC-8 IOL eyes and fellow eyes in the test group for mean monocular DCIVA (logMAR) will be performed using a two-sample t-test at $\alpha = 0.05$ (two-sided). The null hypothesis is that the mean acuity for the IC-8 IOL eyes is greater (i.e., worse) than or equal to that for the fellow eyes. The alternative hypothesis is that the mean for the IC-8 IOL eyes is less (i.e., better) than that for the fellow eyes. Formally put as follows:

$$H_0: \mu_T \ge \mu_C$$
$$H_A: \mu_T < \mu_C$$

Where μ_T is the mean logMAR acuity from the IC-8 eyes and μ_C is the mean acuity from the fellow eyes.

The statistical success criterion is when H_0 is rejected by a p-value less than 0.05, demonstrating the mean DCIVA from IC-8 eyes is statistically superior to the mean DCIVA from the control eyes.

- b. At least 50% of IC-8 IOL eyes should achieve DCIVA of logMAR 0.2 or better [clinical success criteria].
- 5. Monocular photopic distance-corrected depth of defocus (measure only negative direction from zero) of the IC-8 IOL eyes (at 3 months):

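### With non-randomised arms, the protocol decides binocular UCDVA non-inferiority on an unadjusted t-test and gives its planned adjusted analysis no stated role in success

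*Combined protocol and SAP*

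**What the plan says.** Section 9.1 states that enrolment into the two groups is not randomised. The reason given is that an extended-range lens is already marketed and "patients who desire an extended depth focus should have the opportunity to receive this technology". To allow comparison, it asks that "the two groups should have similar distributions on age, sex, race/ethnicity, pupil size and preoperative corneal astigmatism". Table 3 sets enrolment targets by astigmatism group only. Section 7.0 leaves further control of baseline imbalance during enrolment to the SAP.

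For binocular UCDVA at 6 months, Section 18.2.1 item 3a says: "The comparison between test and control groups for mean binocular UCDVA (logMAR) will be performed using a t-test for non-inferiority". The margin is 0.1 logMAR, alpha is 0.05 one-sided, and success is p < 0.05. No covariate or stratum is named. Item 3b adds "At least 50% of test subjects achieve 0.1 or better logMAR [clinical success criteria", which concerns the test arm alone.

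Section 18.2.3 provides the adjustment: "As a supplemental analysis for all primary endpoints, propensity score methods will be used to adjust for potential imbalance in measured baseline characteristics". The primary analyses are repeated in propensity-score quintiles, and results are given for each stratum and combined. It states no success criterion and no rule for a result that disagrees with the t-test; details are left to the SAP. Section 18.0 says: "Other statistical comparisons in the additional analyses and supportive analyses should not be used for the purpose of claims".

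**The concern.** In a non-randomised comparison the t-test estimates the lens effect plus any baseline difference between arms that predicts acuity. Its 5% error rate holds only if that second part is zero. Section 9.1 treats balance on five factors as the condition for comparing the groups, yet the deciding test does not use them.

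The size and direction of any imbalance are unknown. If it favours the test arm, a lens pairing worse by the full margin can pass. If it favours the control arm, the test is too strict and an acceptable pairing can fail.

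UCDVA is the most exposed of the three binocular co-primaries. UCIVA and UCNVA also need a responder rate at least 25% above control (items 1b and 2b); UCDVA has no between-group responder rule.

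**Working it through.** **The plan's own figure.** Section 7.0 allows for about 10% attrition and "another 5% disqualification rate for the first implanted eye". 300/(0.90 × 0.95) = 350.9 and 100/(0.90 × 0.95) = 117.0, consistent with the 355 and 120 to be enrolled. The protocol gives no SD, expected difference or power for UCDVA, so that calculation cannot be reproduced.

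**Inputs.** From the protocol: 300 v 100 completers, margin 0.1 logMAR, one-sided 0.05, the 50% rule. Assumed: imbalance 0.1 to 0.5 SD, correlation with UCDVA 0.3 (0.1 or 0.2 each when five factors differ), SD 0.10 to 0.20 logMAR, control mean 0.0 to 0.05 logMAR.

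**Closed form for the t-test.** SE = √(1/300 + 1/100) = 0.1155 SD. Bias = imbalance × correlation. With the true deficit at the margin, P(pass) = P(Z > 1.645 − bias/SE).

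| Imbalance (SD, + favours test) | Bias (SD) | False non-inferiority |
|---|---|---|
| 0 | 0 | 5.0% |
| +0.1 | 0.03 | 8.3% |
| +0.25 | 0.075 | 16.0% |
| +0.5 | 0.15 | 36.5% |
| −0.25 | −0.075 | 1.1% |
| −0.5 | −0.15 | 0.2% |

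A bias of 0.15 SD is 0.015 to 0.03 logMAR at SD 0.10 to 0.20. Section 18.2.2 equates 0.12 logMAR with 6 letters, so this is about one letter.

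**Adjusted analyses, simulated** (five covariates in the model, one imbalanced, correlation 0.3). ANCOVA error is 4.7-5.1%. Quintiles, merging strata with fewer than 5 subjects in an arm, give 3.1-6.5%. An unadjusted pass with an ANCOVA fail occurs in 1.3%, 11% and 30% of trials at 0, +0.25 and +0.5 SD.

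**All five factors imbalanced:**

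| Imbalance, correlation each | t-test | ANCOVA | Quintiles |
|---|---|---|---|
| 0.25 SD, 0.1 | 30.0% | 5.4% | 6.6% |
| 0.5 SD, 0.1 | 70.3% | 5.6% | 9.4% |
| 0.25 SD, 0.2 | 68.7% | 5.2% | 7.6% |
| 0.5 SD, 0.2 | 99.7% | 5.0% | 13.7% |

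These are stress tests of the methods, not forecasts; one of the five factors, astigmatism, has enrolment targets in Table 3. If one covariate effect is curved, linear ANCOVA error is 3.1-7.6%.

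**Effect of the 50% rule** (one factor, +0.5 SD, correlation 0.3), as the chance of passing both criteria:

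| Control mean (logMAR) | SD 0.10 | SD 0.15 | SD 0.20 |
|---|---|---|---|
| 0.00 | 36% | 36-37% | 36-37% |
| 0.03 | 2% | 15% | 25% |
| 0.05 | 0% | about 0.5% | 6% |

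**Effect of the first-eye gate** (Section 7.3). If the planned 5% disqualification were all for UCDVA, truncating the worst 5% leaves 1 − 1.645 × 0.1086 − 0.1086² = 0.81 of a first-eye mean difference. Simulated false non-inferiority is then 14-15% at +0.25 SD and 31-32% at +0.5 SD.

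**The opposite direction.** At a true deficit of 0.05 logMAR and 0.5 SD imbalance against the test arm, power is 0.47 for the t-test and 0.91 for ANCOVA at SD 0.15, and 0.21 and 0.72 at SD 0.20.

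**The case against.** **The SAP may settle it.** Section 18.0 presents itself as highlights and sends full methods to the SAP; 18.2.3 does the same. A reader might infer that the adjusted analysis definitely has no decision role. The documents at hand support only that the protocol states none. That stands as a limit.

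**The claims bar may not apply.** A reader might infer that the Section 18.0 sentence excludes the propensity analysis from claims. It names additional and supportive analyses, which are the labels used in 18.2.4. Section 18.2.3 is separate and labelled supplemental, so the reach of the sentence is unclear. The point does not need it: the criteria in 18.2.1 never mention the adjusted result.

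**Allocation by preference is not documented.** Section 9.1 gives a reason for not randomising, and the protocol text describes no assignment procedure. The synopsis describes the whole study population as wanting presbyopia mitigated. Preference-driven imbalance is possible but not shown.

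**Other safeguards exist.** Both arms share the same eligibility limits on acuity potential and pathology and the same first-eye gate, including its best-corrected requirement, which the gate calculation does not model. These narrow the spread of acuity and could lower the assumed correlation. The masked examiner deals with measurement bias, not selection. The within-subject best-corrected acuity test is free of between-arm confounding, but it is monocular and corrected, so it does not show the effect of the refractive target in the IC-8 eye.

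**The 36% is a corner case.** It needs a deficit exactly at the margin, 0.5 SD imbalance, correlation 0.3 and a control mean near 0.0. This is right, and the 50% rule can remove most of the error at higher control means. The figure is not an expected error rate.

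**Conclusion.** The concern holds for the protocol text. Allocation is non-randomised, an unadjusted t-test and a test-arm-only rule decide binocular UCDVA, and an adverse adjusted result would not change the outcome. Under the stated assumptions false non-inferiority is 8%, 16% or 36% at 0.1, 0.25 or 0.5 SD imbalance favouring the test arm. At 0.5 SD it falls to 2-25% or 0-6% where the control mean is 0.03 or 0.05 logMAR. ANCOVA holds it near 5% when covariate effects are linear.

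It does not follow that the trial is biased, or in which direction. Nor does it follow that adjustment would remove all bias: it handles measured factors only, and an unmeasured effect of preference would remain. This is an improvement that should be made, held with medium confidence because the SAP was not available.

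**What to change.** In 18.2.1 item 3a and 18.2.3, make one prespecified adjusted comparison decisive for binocular UCDVA: the one-sided 95% upper limit of the adjusted difference must lie below 0.1 logMAR. Report the unadjusted t-test as supportive.

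- **Preferred:** ANCOVA on arm plus the five factors listed in Section 9.1, or the SAP's propensity covariates. State which eye and which pupil condition supply the values.
- **Acceptable:** the planned quintile estimate, merging any stratum with fewer than 5 subjects in either arm. It leaves more residual bias, and the smallest quintile averages only about 3 controls when all five factors differ by 0.5 SD.
- **Minimum:** require both analyses to pass. This needs no alpha adjustment, but it keeps the excess strictness when imbalance runs against the test arm.

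Apply the same rule to UCIVA and UCNVA for consistency, and state whether the 25% is percentage points. At 0.5 SD and correlation 0.3 with no true difference, their t-test alone passes 25% of the time. Adding the responder rules cuts this to at most 0.06% if percentage points are meant, but it can reach 13.9% if the 25% is relative. If the SAP already gives the adjusted result a decision role, align 18.2.1 and 18.2.3 with it.

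**Cost.** Wording only, on baseline data already collected. The standard error is about 0.95 to 1.10 times the unadjusted one for ANCOVA, and up to about 1.3 times for quintiles under strong imbalance. If one covariate of no prognostic value is imbalanced by 0.5 SD, ANCOVA power at a 0.05 logMAR deficit is 0.88 against 0.90 (SD 0.15), or 0.68 against 0.70 (SD 0.20). Check the SAP's sample-size text against the new analysis.
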